1.5. Benefit-Risk Assessment

The safety of PMN310 will be assessed throughout the study by monitoring AEs, using criteria proposed by Sibille et al., 2010, clinical laboratory assessments, vital sign measurements, physical and neurological examinations, 12-lead ECG measurements, and magnetic resonance imaging (MRI) evaluations.

There are no expected direct health benefits to subjects in Study PMN310-101. The safety, tolerability, and PK data collected in Study PMN310-101 will provide initial data supporting the evaluation of PMN310 in patients with AD.

2. STUDY OBJECTIVES AND ENDPOINTS

2.1. Study Objectives

2.1.1. Primary Objectives

• To assess safety and tolerability of escalating doses of PMN310 when administered as a single IV infusion in healthy volunteers

2.1.2. Secondary Objectives

To assess the single dose PK of PMN310

2.1.3. Exploratory Objectives

- To assess the immunogenicity of PMN310 following single dose administration
- To assess biomarkers in healthy subjects

2.2. Study Endpoints

2.2.1. Primary Endpoints

• Adverse events (AEs), clinical laboratory tests (clinical chemistry, hematology, urinalysis), physical and neurological examinations, vital signs, and 12-lead ECGs

2.2.2. Secondary Endpoints

- Serum PK: maximum observed concentration (C_{max}), time to C_{max} (T_{max}), area under the curve from Time 0 to last sampling time (AUC_{0-t}), area under the curve from Time 0 to infinity ($AUC_{0-\infty}$), terminal half-life ($t_{1/2}$), volume of distribution (Vd), clearance (CL)
- Cerebrospinal fluid (CSF) drug concentrations

2.2.3. Exploratory Endpoints

- Incidence and titers of ADAs
- Residual and unused serum and CSF samples will be stored for future use for the measurement of biomarkers

3. STUDY DESIGN

3.1. Design Characteristics

This is a randomized, placebo-controlled, single ascending dose clinical study of PMN310 in healthy adult volunteers. The study aims to establish the safety, tolerability, and PK of a single IV infusion of PMN310.

Subjects who provide written informed consent and meet all eligibility criteria will be admitted to the study clinic on Day -1 (i.e., the day prior to dosing with PMN310 or placebo). Subjects will be domiciled for 4 nights with standardized meals provided during inpatient stay. On Day 1, subjects will be randomly assigned to receive either a single infusion of PMN310 or placebo (6:2 ratio). After randomization on Day 1, study drug will be administered followed by the collection of safety, tolerability, and PK data for 12 weeks postdose (outpatient follow-up period). Following completion of the postdose outpatient follow-up period, subjects may return for an optional follow-up visit to evaluate PK, ADA, and exploratory biomarkers, if warranted by previous data. The decision to recommend the optional follow-up visit will be made by the Sponsor and communicated to the Investigator who will notify the subject about the timing of the optional visit.

All dose cohorts will have lumbar punctures (LPs) performed on Day 3 and Day 29. The timing of additional LPs will be based on available serum PK and CSF concentrations of PMN310 from prior cohorts. The timing of LPs will be communicated to the Investigator who will inform the subject. No subject will have more than 3 total LPs.

A detailed summary of the schedule of events is available in Appendix 1.

3.1.1. Dose Escalation Rules

[figure not shown]
Each dose cohort will consist of 8 subjects (6:2; PMN310:placebo). To evaluate the short term safety and tolerability of PMN310, each cohort will enroll a sentinel group of 2 subjects (1:1, PMN310:placebo) who will be dosed prior to dosing the remaining 6 subjects in the cohort (5:1, PMN310:placebo). The first two sentinel subjects for Cohort 1 (age < 50) will have MRIs performed and read locally. The SRC will review all safety data collected through 48 hours postdose from the 2 sentinel subjects to determine the acceptability of proceeding with dosing of the remaining 6 subjects in the cohort. Additional details on the SRC are provided in Section 3.1.2.

Dose escalation to the next cohort will only occur after approval by the SRC. The SRC will determine the acceptability of proceeding with enrollment of the next cohort based on review of safety and any available PK data at the time of review through 7 days postdose for a minimum of 6 of 8 subjects per cohort. Doses to be evaluated are presented in Section 5.2.1.

In the event that important safety concerns are observed at any time during the study, administration of study drug will be paused, subjects in the subsequent cohort(s) will not receive further study drug until further review of the safety data has occurred, and subsequent recommendations and approval have been provided by the SRC. Dose escalation/stopping rules are detailed in Section 5.5.

A schematic illustrating the study design is provided in Figure 1.

Figure 1: PMN310-101 Study Schema Per Cohort

3.1.2. Safety Review Committee

The SRC will be responsible for the review of safety and any available PK data at the time of review, and making determinations regarding the acceptability of proceeding with dosing of the remaining 6 subjects in a cohort (based on review of sentinel subjects) and dose escalation to the next cohort. The SRC will be comprised of the Study Investigator, Medical Monitor, and Sponsor Medical Director. At a minimum, the SRC will review safety data assessments collected 48 hours after the sentinel subjects have been dosed in each cohort and ≥ 7 days post-dose for a minimum of 6 of 8 subjects per cohort prior to each dose escalation. The SRC charter will specify operational details pertaining to roles and responsibilities, data to be reviewed, review frequency, and reporting.

4. STUDY POPULATION

4.1. Inclusion Criteria

Subjects must meet all of the following inclusion criteria to be eligible for this study:

- 1. Male and females, 18 to 65 years of age, inclusive, at time of Screening.
 - a. Female subjects of childbearing potential must not be breastfeeding and must have no plans to become pregnant during the course of the study through 120 days after infusion of study drug. Female subjects of childbearing potential who are heterosexual must agree to use 1 of the following methods of contraception considered to be highly effective (i.e., results in < 1% failure rate when used consistently and correctly) from Screening through 120 days after the last dose of study drug:
 - Intrauterine device or intrauterine system in place for at least 3 months prior to first dose.
 - Partner has had a vasectomy ≥ 4 months prior to participation. Vasectomy in the
 partner is considered to be highly effective only if the partner is the sole sexual
 partner of the female subject of child-bearing potential and the vasectomy (as
 communicated to the subject by the vasectomized partner) was medically assessed
 as surgically successful.
 - Stable hormonal contraception associated with inhibition of ovulation (including by not limited to approved oral, transdermal, or depot regimen) for at least 3 months prior to first dose.
 - b. Female subjects of non-childbearing potential must have evidence from their medical history indicating that they are not of childbearing potential and must not currently be breastfeeding. Accepted evidence (self-reported medical history is acceptable) includes:
 - History of sterilization surgery, including tubal ligation, tubal occlusion, hysterectomy, bilateral salpingectomy, bilateral oophorectomy.
 - Postmenopausal status (12 months with no menses and no alternative cause).
 Postmenopausal status will be confirmed with a follicle-stimulating hormone (FSH) test at Screening (FSH > 40 mIU/mL). If there is any doubt about a female subject's post-menopausal status the subject must use a form of highly effective birth control as noted in Inclusion Criterion 1a.
- 2. Any non-vasectomized male subjects must agree to use barrier contraceptives (male or female partner condom, diaphragm, cervical cap, sponges) plus spermicide for 200 days after dosing. No restrictions are required for a vasectomized male provided his vasectomy was performed 4 months or more prior to study start. A male who has been vasectomized less than 4 months prior to study start must follow the same restrictions as a non-vasectomized male.
- 3. Males must not donate sperm for at least 200 days after dosing.

- 4. Female subjects must agree not to donate or preserve eggs (ova) for 120 days after dosing.
- 5. Medically healthy with no clinically significant or relevant abnormalities in medical history, physical exam, vital signs, ECG, or laboratory evaluations (hematology, chemistry, and urinalysis) as assessed by the Investigator. At the Investigator's discretion, laboratory evaluations may be repeated at Screening or Baseline (pre-dose) to assess clinical significance of abnormalities prior to dosing.
- 6. Confirmed to have acceptable venous access for blood collections and IV dosing administration of study medication.
- 7. Has provided written informed consent.
- 8. Body mass index is between 18 and 32 kg/m² (inclusive).
- 9. Screening MRI reveals normal appearance of the brain parenchyma, normal spacing of ventricular system and cisternal spaces and is without any significant abnormality, including, but not limited to evidence of prior microhemorrhages, lacunar infarcts, hemorrhage, or infarct > 1cm³, cerebral contusion, encephalomalacia, aneurysm, vascular malformation, subdural hematoma, hydrocephalus, space occupying lesion (e.g., abscess or brain tumor such as meningioma).

4.2. Exclusion Criteria

Subjects having any of the following exclusion criteria are not eligible for this study:

- 1. Current or recurrent disease (e.g., cardiovascular, neurological, renal, liver, gastrointestinal, malignancy, autoimmune disease, or other condition) that could affect the action, absorption or disposition of the investigational product, or could affect clinical or laboratory assessments.
- 2. Clinically significant 12-lead ECG abnormality at Screening. QT interval corrected by Fridericia (QTcF) > 450 milliseconds. ECG may be repeated from the first one collected at Screening. If repeat ECG is ≤ 450 msec, the second ECG may be used to determine subject eligibility. However, if repeat ECG confirms QTcF > 450 msec, the subject is not eligible for this study.
- 3. Systolic blood pressure > 150 bpm or diastolic blood pressure > 90 bpm (measured in supine position after 5 minutes of rest) at Screening. Blood pressure may be repeated from the first assessment collected at Screening. If repeat systolic blood pressure ≤ 150 bpm or diastolic blood pressure ≤ 90 bpm, the second blood pressure may be used to determine subject eligibility.
- 4. Experienced a significant systemic illness, as judged by the Investigator, within 30 days of the first dose of study drug.
- 5. Current or relevant history of physical or psychiatric illness, any medical disorder that may require treatment or make the subject unlikely to fully complete the study, or any condition that presents undue risk from the investigational product or procedures.
- 6. Currently using any medication (including over-the-counter, herbal or homeopathic preparations) except for acetaminophen as needed for miscellaneous aches and pains.

- 7. History of alcohol abuse and/or illicit drug use within 12 months prior dosing or a smoking history (use of tobacco products).
- 8. Unwilling to refrain from ingesting alcohol from Screening through Day 15 and unwilling to limit alcohol use to ≤ 7 drinks per week from Day 15 for the duration of the study; 1 drink is 5 ounces (150 mL) of wine, 12 ounces (360 mL) of beer, or 1.5 ounces (45 mL) of hard liquor.
- 9. Positive urine drug screen for drugs of abuse or cotinine, or positive serum alcohol at Screening or Day -1.
- 10. Any significant concomitant disorder, including active bacterial, fungal, or viral infection, incompatible with participation in the study.
- 11. History of prior malignancy (except adequately treated non melanoma skin cancer or carcinoma in-situ of the cervix).
- 12. Documented history of human immunodeficiency virus (HIV) antibody, or tested positive for hepatitis B surface antigen (HBsAg) or hepatitis C virus (HCV) antibody at Screening.
- 13. Donated blood or blood products (e.g., plasma, platelets) within 28 days prior to first dose.
- 14. Received an investigational agent within the last 30 days or 5 half-lives (if known) prior to Screening, whichever is longer.
- 15. Contraindication to brain MRI.
- 16. Contraindication to undergoing LP including: sensitivity to local anesthetic, international normalized ratio (INR) > 1.4 or other coagulopathy, platelet cell count of < 120,000/μL, infection at the desired LP site, current use of anti-coagulant medication except for low dose aspirin, degenerative arthritis, spinal scoliosis, back surgery, suspected increased intracranial pressure on history or neurologic exam, non-communicating hydrocephalus or intracranial mass, or prior history of spinal mass or trauma and/or other known clinically significant spinal abnormalities.
- 17. Inability to undergo venipuncture or tolerate venous access.
- 18. Indication of potential suicidality risk as identified by the following:
 - a. Lifetime history of recurrent serious or recurrent suicide behavior.
 - b. History of suicide behavior in the past "5" years as indicated by a "yes" response to any suicide behavior question on the Columbia-Suicide Severity Rating Scale (C-SSRS) Baseline Screening version.
 - c. Suicidal ideation with intent or plan within the previous "12" months with a "yes" response to Item 4 or 5 on the C-SSRS Baseline Screening version.
- 19. Any of the following: clinically significant abnormalities on vital signs, physical exam, or laboratory testing at Screening and Baseline (pre-dose) per Investigator discretion.

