# 8.6 Vital Signs and Anthropometrics

CONFIDENTIAL Page 24 of 32

Vital signs data collected include systolic blood pressure (SBP) (mmHg), diastolic blood pressure (DBP) (mmHg), pulse rate (bpm), respiratory rate (breaths/min), oral temperature (C), weight (kg), and BMI (kg/m²) and will be summarized descriptively for continuous data by visit and timepoint for the observed value as well as for the change from baseline value, where available.

A categorical summary table describing the n (%) of subjects meeting the below thresholds at any post-baseline visit/timepoint will be generated.

Vital Sign Pre-Defined Thresholds

- SBP > 180 mmHg (High)
- SBP  $\leq$  90 mmHg (Low)
- DBP > 110 mmHg (High)
- DBP  $\leq$  50 mmHg (Low)
- SBP increased by  $\geq 30$  mmHg from baseline
- SBP decreased by  $\geq 30$  mmHg from baseline
- DBP increased by  $\geq 20$  mmHg from baseline
- DBP decreased by  $\geq 20$  mmHg from baseline

All vital signs data will be presented in a by-subject listing.

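### Exclusion 8 joins its two alcohol conditions with *and*, so as written it excludes only a subject who refuses both; the repeat clause of Exclusion 3 is also ambiguous

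*Protocol*

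**What the plan says.** Protocol Section 4.2 makes each criterion sufficient by itself: "Subjects having any of the following exclusion criteria are not eligible for this study".

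Exclusion 8 reads "Unwilling to refrain from ingesting alcohol from Screening through Day 15 and unwilling to limit alcohol use", the limit being 7 drinks per week from Day 15 to the end of the study. The synopsis has the same wording.

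Exclusion 3 applies at Screening to "Systolic blood pressure > 150 bpm or diastolic blood pressure > 90 bpm". It then allows a repeat: "If repeat systolic blood pressure ≤ 150 bpm or diastolic blood pressure ≤ 90 bpm", in which case "the second blood pressure may be used to determine subject eligibility". Exclusion 2, just above it, allows a repeat ECG in the same way but adds that a subject whose repeat confirms a QTcF over the limit is not eligible. Exclusion 3 has no matching sentence. The synopsis again repeats the text.

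On units, SAP Section 8.6 has "Vital signs data collected include systolic blood pressure (SBP) (mmHg), diastolic blood pressure (DBP) (mmHg), pulse rate (bpm"), so the SAP keeps bpm for pulse and mmHg for pressure.

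**The concern.** The two halves of Exclusion 8 cover consecutive periods, and the evident purpose is a two-stage restriction that every participant accepts in full. An exclusion that needs refusal of both stages does not express that purpose.

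The early period matters most for the data. It runs from Screening across dosing and the laboratory visits on Days 3, 8 and 15 (Protocol Appendix 1). The chemistry panel in Section 7.1.9 includes ALT, AST and GGT, and clinical chemistry is part of the primary endpoint (Section 2.2.1). Alcohol use in that window could be a competing explanation for a liver-enzyme change in an active group of 6.

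For Exclusion 3, the same repeat reading can be taken to support either outcome. That is undesirable for a rule that may be applied at up to four sites.

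**Working it through.** No sample-size, power or error-rate figure is involved, so the check is a truth table for each criterion, followed by a search for other text that would close the gap.

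**Exclusion 8.** Let A = unwilling to abstain through Day 15, and B = unwilling to keep to 7 drinks per week or fewer afterwards.

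| A | B | Excluded as written (A *and* B) | Excluded with *or* |
|---|---|---|---|
| no | no | no | no |
| no | yes | no | yes |
| yes | no | no | yes |
| yes | yes | yes | yes |

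As written, 1 of 4 combinations is excluded, which is 1 of the 3 that contain a refusal. With *or*, 3 of 4 are excluded, which is all 3 that contain a refusal.

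Other text that might cover the two missed patterns:
- Exclusion 7 concerns a history of alcohol abuse, not willingness to restrict intake.
- Exclusion 9 excludes on a positive serum alcohol at Screening or Day -1. It detects recent use at two time points and says nothing about intentions to Day 15 or later.
- Section 5.7.1 prohibits medications and does not mention alcohol.
- The serum alcohol screens on Days 8 and 85 come after dosing, so they cannot affect eligibility.

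None of these closes the gap, and the synopsis offers no correctly worded version to fall back on.

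**Exclusion 3, repeat clause.** The readings below are illustrative, in mmHg, and are not from the documents.

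| Repeat reading | Systolic ≤ 150 | Diastolic ≤ 90 | Clause met as written (*or*) | Clause met with *and* | Excluded if judged by the first sentence |
|---|---|---|---|---|---|
| 145/85 | yes | yes | yes | yes | no |
| 155/85 | no | yes | yes | no | yes |
| 145/95 | yes | no | yes | no | yes |
| 155/95 | no | no | no | no | yes |

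As written, the clause is met in 3 of 4 outcomes; with *and*, in 1 of 4. In the two mixed outcomes the clause lets the repeat be used while the criterion's own first sentence still excludes that repeat. The result depends on whether meeting the clause is itself the pass condition or only permission to judge the second reading. The text does not say which.

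**Unit.** All four limits in Exclusion 3 are printed in bpm, against mmHg in the SAP.

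**The case against.** The best defence of Exclusion 8 is practical. Its intent is plain, a site would be expected to apply both restrictions, and serum alcohol is tested at Screening, on Day -1 and again on Day 8, inside the abstinence window. This reduces the likely harm. It does not close the gap, because the tests detect use rather than unwillingness, and the criterion as worded still gives the wrong answer for two of the three refusal patterns.

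For Exclusion 3, a reader might infer that the repeat clause plainly admits someone with, say, 155/85. The documents do not support that. The clause only allows the second reading to be used in deciding eligibility, and against the first sentence 155/85 is still excluded. The absence of a sentence like that in Exclusion 2 could be a difference of style. The ambiguity stands; a definite admission does not. The bpm unit is a typographical error that admits nobody.

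A reader might also infer the same fault in Exclusion 19, which refers to "laboratory testing at Screening and Baseline (pre-dose) per Investigator discretion" and could be read as needing an abnormality at both times. That does not hold. Here *and* can naturally mean at each visit. In addition, Inclusion 5 (Section 4.1) requires the absence of clinically significant abnormalities in vital signs, physical examination and laboratory results, and all inclusion criteria must be met. Eligibility is confirmed on Day -1, when these assessments are repeated (Section 6.2.1.1). An abnormality at one time point alone already bars the subject, so the full criteria admit nobody extra.

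**Conclusion.** The point holds for Exclusion 8: its connector is wrong, the error appears in both places where the criterion is printed, and nothing else in the protocol compensates. Exclusion 3 has an ambiguous repeat clause and a wrong unit, which are secondary drafting faults.

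The importance is low. One wrongly enrolled subject would be 1/6 = 17% of an active dose group, but a reader should not take that as an estimated effect. The documents give no likelihood of such an enrolment, and the subject could equally fall in the placebo group, which is pooled across cohorts. Continuous laboratory and vital-sign results are also summarised as change from baseline (SAP Sections 8.3 and 8.6), and no hypothesis testing is planned (SAP Section 6.6).

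The conclusion rests on the text of protocol v2.0. SAP Section 3.1 cites three clarification letters, dated 9 October, 26 October and 16 November 2023, all later than that version. They were not available and may already correct the wording.

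**What to change.** First check whether the three clarification letters deal with these criteria. If they do not, make these changes in both Section 4.2 and the synopsis:
- **Exclusion 8:** change *and* to *or* between the two unwillingness conditions.
- **Exclusion 3:** reconcile the repeat clause with the criterion's first sentence by requiring both repeat values to be within the existing limits, and add a sentence on a confirmed high value in the style of Exclusion 2. Replace bpm with mmHg.

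Exclusion 19 needs no change on this account. No limit is altered.

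The cost is a few words, with no effect on sample size, data collection or analysis. Protocol Section 11.3 lists subject-selection criteria among the changes that need an amendment with ethics approval, so the edits can go into the next amendment. If enrolment is already complete, the clinical study report should state how sites applied Exclusion 8. A subject admitted under its literal wording would have no unmet criterion to show in the eligibility listing described in SAP Section 7.1.

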5. STUDY TREATMENTS

5.1. Identification and Description of Study Drug

5.1.1. PMN310

Additional information about PMN310 drug product is available in the Investigator's Brochure.

5.1.2. Placebo

Placebo will consist of 100 mL 0.9% NaCl.

5.2. Study Drug Preparation and Administration

5.2.1. PMN310

Study medication will be prepared at the study clinic by an unblinded pharmacist (or designee) based on an individual subject's randomization or assigned treatment. Once prepared, blinded IV drug for infusion will be dispensed to staff who will administer study drug. Specific instructions for preparation and administration of study medication will be provided in the Pharmacy Manual.

PMN310 will be administered as a single IV infusion over 60 minutes in 0.9% NaCl, adjusted to a total volume of 100 mL, followed by a 15 minute 0.9% NaCl flush. The complete infusion will consist of the IV infusion and the flush following the IV infusion.

The following dose level cohorts are planned to be evaluated: 175 mg (starting dose level), 350 mg, 700 mg, 1400 mg, and 2800 mg (optional cohort). The rationale for selecting these dose levels is provided in Section 1.4.

